## 1. PURPOSE OF THE STUDY

---

### a. Brief Summary

The purpose of this study is to assess the safety and ease of use of a trocar placement access device (TPAD, Tautona) for laparoscopic surgery. 10 patients will undergo laparoscopic surgery as planned, with their surgeon using the TPAD device to guide Veress needle insertion and primary trocar placement while gaining access to the peritoneal cavity. Surgeons will complete a questionnaire following use of the TPAD to evaluate the device feasibility. Ten patients will undergo standard of care without use of the TPAD device and also complete surveys.

---

### b. Objectives

We hope to assess device feasibility and efficacy of the Tautona TPAD for clinical use.

---

### c. Rationale for Research in Humans

The purpose of the study is to measure ease-of-use by surgeons in human patients. therefore, human patients are needed.

---

## 2. STUDY PROCEDURES

---

### a. Procedures

Surgeons will identify patients scheduled to undergo laparoscopic surgery procedures and notify study staff. The patient will be met in the pre- operative holding area and informed consent will be obtained.

Patients will be randomized via block randomization.

Clinical information will be collected from participating patients including age, sex, demographic, past medical and surgical history, medications, allergies, diagnosis, and planned procedure. Clinical data will be de- identified and stored on a password protected spreadsheet on a PHI- safe server.

The surgeon will utilize the TPAD device to assist with Veress needle insertion (standard of care) to obtain access to the peritoneal cavity. The device will also be used to guide primary trocar placement.

Following induction of general anesthesia, the patient is prepped and draped in sterile fashion. Local anesthetic is infiltrated at the planned incision site and an incision is made with a scalpel. These steps are the same in any laparoscopic procedure. Next, the sterile TPAD, which is connected to a suction source, is centered over the incision, and the suction cups activated to non-invasively grasp the skin. The TPAD is pulled upward, and the Veress needle is advanced through the incision into the peritoneal cavity. Once the needle enters the cavity, the abdomen is insufflated as per usual standard of care. Once insufflated, the veress needle is withdrawn while maintaining the TPAD's suction on the skin. The primary trocar is then advanced through the incision into the abdominal cavity. The suction is then released and the TPAD taken away from the operating field.

The time needed to obtain laparoscopic access and the time needed for trocar placement will be recorded. Non-identifiable photos and/or video may be taken of the TPAD device during use. Acquired digital images may capture a portion of the patient's skin, however if a patient has any identifying features such as scars or tattoos, these areas will be cropped out of the images, or if this is not possible, no images will be recorded of that patient. There will be no other alterations to the planned surgery and it will proceed as planned. Following surgery, the surgeon will complete a questionnaire. Any adverse events will be recorded by medical record review.

Patients will undergo routine postoperative care as indicated by their surgery. no additional visits will be required due to their being enrolled in the study. The patient will participate in a questionnaire and may take non-identifiable photographs of the portion of the patients skin where the TPAD device acts, as described above.

---

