**g. Study Endpoint(s)**

The study will terminate after 10 patients have been enrolled and have undergone surgery with use of the study device and 10 patients have undergone the standard of care and completed the survey. The primary outcome measure is device feasibility as measured by a surgeon questionnaire, which is completed at the end of every surgery. Secondary outcome measures include the time needed to obtain laparoscopic access using the device, as well as monitoring for adverse events. Another secondary outcome measure includes patient questionnaire to assess satisfaction.

If there is clear evidence of a lack of device feasibility through surgeon questionnaire review, or if there are any adverse events recorded that are related to the device and which endanger the health of a patient, the project leader will evaluate this information and decide whether any modifications or termination of the protocol are indicated.

---

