**g. Recruitment Details**

The surgeon will identify patients scheduled for laparoscopic surgery from their schedule and invite them to participate. If they are agreeable, study staff will be notified by the surgeon. The study staff will then meet the patient in the pre-operative area before their surgery to discuss the study and to obtain consent.

---

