Pilot Study to Establish Safety and Ease of Use of a TauTona Pneumoperitoneum Assist Device (TPAD) for Laparoscopic Surgery

NCT04392635

August 19, 2024

Statistical Analysis Plan

Statistical Methods

For surgeon and patient questionnaire answers, a Wilcoxon test will be performed for each answer against a theoretical median of 4.0 (best). Since the insertion of the Veress needle should not significantly impact the final outcome of the entire laparoscopic procedure, analysis assumes that the theoretical median for each answer should be 4.0. Further, the standard of care is assumed to provide the current best care, so its theoretical median should be 4.0.

Determination of Sample Size

There were no statistically powered sample size requirements for this study. Based on the end points, the sample size of 15 for each group would be sufficient to determine bruising and the ability of the TPAD device to function as intended as compared to the control group.

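### The surgeon who chooses whom to invite also knows the arm and scores the primary outcome, and no allocation concealment is described, so selection bias cannot be ruled out

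*Protocol*

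**What the plan says.** - **Allocation.** Protocol 2.a gives one sentence: "Patients will be randomized via block randomization". Block size, fixed or varying blocks, stratification, list holder, concealment and time of assignment are not given in either document.
- **Selection.** Protocol 8.g: "The surgeon will identify patients scheduled for laparoscopic surgery from their schedule and invite them to participate". Consent comes later and from others: "The study staff will then meet the patient in the pre-operative area before their surgery to discuss the study and to obtain consent".
- **Entry.** Protocol 2.a: "The surgeon will utilize the TPAD device to assist with Veress needle insertion". Blinding is not mentioned, and a surgeon holding the device cannot be blind to it.
- **Scoring.** Protocol 2.g: "The primary outcome measure is device feasibility as measured by a surgeon questionnaire, which is completed at the end of every surgery".
- **Partial limits.** Protocol 8.h excludes BMI above 35, suspected or confirmed peri-umbilical adhesions, umbilical or peri-umbilical hernia, compromised skin, and any contraindication to blind Veress passage. Protocol 8.i has the surgeon tell study staff about every patient who meets the inclusion criteria, and rules out collecting health information before enrolment.
- **Size.** Protocol 2.g: "The study will terminate after 10 patients have been enrolled and have undergone surgery with use of the study device", with 10 more on standard of care, so 20 (also in 1.a). Protocol 8.a plans 30, and the SAP says "the sample size of 15 for each group would be sufficient to determine bruising".
- **Analysis.** The SAP tests each questionnaire answer against a fixed median of 4.0. It describes no between-arm test and no adjustment for difficulty of entry.

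**The concern.** One role controls who enters the trial, sees each allocation as it is used, and supplies the primary outcome. The invitation comes before the arm is assigned, which is the step at which selection can act. Blocked lists return to balance at the end of each block, so someone who has seen the earlier allocations can do better than chance on the next one. Difficulty of Veress entry varies between patients, and the surgeon knows a good deal about it from the operating list.

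If invitations came to depend on the arm expected next, the two groups would differ before the device was used. The questionnaire answers and the access time would then partly reflect which patients were chosen. With 10 or 15 patients per arm, a few such choices are a noticeable share of the data.

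**Working it through.** The plan gives no figure for predictability, block size or power ("There were no statistically powered sample size requirements for this study"), so there is nothing to reproduce. Block sizes and numbers of surgeons below are assumptions. The protocol speaks of surgeons in the plural but gives no number.

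**1. One recruiter who sees every earlier allocation and knows the block size.** For 1:1 blocks of size 2m, guessing the arm with more places left gives an expected number correct per block of m + 2^(2m−1)/C(2m,m) − 1/2. Dividing by 2m gives the accuracy p. The share of allocations known with certainty is 1/(m+1). If an easier case were invited whenever one arm was guessed and a harder case otherwise, the proportion of easier cases would be p in that arm and 1−p in the other, a gap of 2p−1.

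| Block size | Expected correct per block | p | Certain | Worst-case gap, 2p−1 |
|---|---|---|---|---|
| 2 | 1 + 2/2 − 0.5 = 1.5 | 75.0% | 50% | 50 points |
| 4 | 2 + 8/6 − 0.5 = 2.833 | 70.8% | 33.3% | 42 points |
| 6 | 3 + 32/20 − 0.5 = 4.1 | 68.3% | 25% | 37 points |
| 10 | 5 + 512/252 − 0.5 = 6.532 | 65.3% | 16.7% | 31 points |
| 20 (one block) | 10 + 524288/184756 − 0.5 = 12.338 | 61.7% | 9.1% | 23 points |
| 30 (one block) | 15 + 536870912/155117520 − 0.5 = 17.961 | 59.9% | 6.25% | 20 points |

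An unpredictable sequence gives 50% correct and none certain.

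**2. Several surgeons sharing one unstratified list, each seeing only their own cases.** This was simulated with 20,000 runs per setting, for totals of 20 and 30 and blocks of 2, 4, 6 and 10. Each case goes at random to one surgeon, who guesses the arm they have personally seen less often and guesses at random on ties.

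| Surgeons | Accuracy across settings |
|---|---|
| 1 | 65.3% to 75.0% |
| 2 | 55.0% to 56.7% |
| 3 | 53.7% to 54.7% |
| 5 | 52.5% to 53.1% |

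The one-surgeon row agrees with the formula. If the list were stratified by surgeon, each surgeon would see a whole list, and the figures in step 1 would apply even with several surgeons.

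**3. In patients.** At 75%, full steering gives a gap of 50 points: 5 of 10 per arm, or 7.5 of 15. At 53% the gap is 2 × 0.53 − 1 = 6 points: 0.6 of a patient in 10, or 0.9 in 15. Both assume steering at every opportunity.

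**4. Effect on the planned test.** The reference value 4.0 is also the best score. An easier case mix in one arm would move that arm's answers towards 4.0, and a harder mix would move the other arm's answers away. A one-sample test does not remove this.

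**5. Why the sample size must be settled first.** If one block of 30 were cut off at 20 patients, the chance of exactly 10 and 10 is C(15,10)²/C(30,20) = 3003²/30045015 = 30%. The chance of 8:12 or worse is 2 × (2927925 + 675675 + 75075 + 3003)/30045015 = 24.5%.

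**The case against.** The strongest reply is that block randomisation is not itself a fault, and that a protocol silent on concealment may still have it. With varying, undisclosed blocks and several surgeons, guessing is barely better than chance. This stands, and it is why the point concerns missing safeguards and not the choice of method.

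A reader might infer that surgeons can guess the next arm and would direct easier abdomens to TPAD. The documents support neither step. Block size, disclosure and number of surgeons are unstated, and nothing indicates that steering would happen or which arm it would favour.

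The exclusions in 8.h also count: they remove the hardest entries. They still admit any BMI up to 35 and previous surgery without suspected peri-umbilical adhesions, and several rest on the surgeon's judgement. Section 8.i can be read as a duty to refer every patient who meets the inclusion criteria. But 8.g makes notification depend on the surgeon's invitation and the patient's agreement, and no record of those passed over is required. Consent by study staff is a partial safeguard that acts after the invitation.

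Finally, this is a pilot with no powered sample size and no specified between-arm questionnaire test, so no formal primary contrast is biased. That limits the consequence but does not remove it. Selection can shift scores within an arm, access time is exposed in the same way, and the SAP's sample-size paragraph itself speaks of judging device function against the control group. The history collected under 2.a would allow imbalance to be described, so it would be too strong to say that nothing could be done afterwards.

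**Conclusion.** The concern holds as a gap in safeguards. The surgeon selects, knows the arm and scores the primary outcome, while no concealment, list custody or invitation log is described. Allocations may be guessable, and selection bias cannot be ruled out.

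Guessing accuracy lies between about 53% and 75% over the settings examined, against 50% by chance. The upper end needs one surgeon and known blocks of 2. The lower end needs five surgeons sharing an unstratified list without exchanging information, and it is not a floor. The corresponding worst-case gap in easier cases is 6 to 50 points. These are sizes under assumption, not estimates of bias in this trial. The documents do not establish that any steering would occur. The change is worth making because it is cheap and because selective invitation cannot be undone once patients are enrolled.

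**What to change.** 1. Reconcile the planned sample: 20 in protocol 1.a and 2.g, 30 in protocol 8.a and the SAP.
2. In protocol 2.a, specify a 1:1 computer-generated list with varying block sizes not disclosed to surgeons, or one block over the reconciled sample. State who generates and holds it, and that neither the surgeon nor the person obtaining consent can see it. Release the arm only after consent and confirmed eligibility, as close to entry as practical.
3. In protocol 8.g, require surgeons to invite consecutive eligible patients and keep a log of those not invited or declining, with the reason. Keep it without identifiers, in line with the limit in 8.i.

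Step 3 matters as much as step 2. A concealed single block of 20 still allows 61.7% correct guesses to one recruiter who sees every past allocation, so the freedom to choose whom to invite has to be narrowed as well.

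The cost is a few protocol sentences, one list and a short log. The device must be on hand for every enrolled case, and the arms may be slightly uneven if enrolment stops early. None of this removes the separate bias from a surgeon scoring with the arm known. If recruitment has already begun, what remains is to document how allocation was done and to tabulate baseline characteristics by arm.

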### a. Potential Risks

#### i. Investigational devices

The TPAD device contacts the abdominal skin through a series of small vacuum powered suction cups. These are only in contact with the skin for a few minutes. The risk of damage to the skin is minimal.

Obtaining peritoneal access with a Veress needle, as well as laparoscopic surgery in general, carries risks including bleeding, damage to underlying structures including injury to bowel or major blood vessels, hernia, infection, scarring, pain, need for additional procedures.

The risks of laparoscopic surgery include:

- Infection
- Bleeding
- Damage to surrounding structures
- Need for additional procedures
- Hernia
- Pain
- Scarring
- Wound healing problems

The risks of veress needle insertion include:

- failed entry
- omental injury
- organ injury
- insertion site infection

The risks of TPAD include:

- skin discoloration/bruising

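### No provision keeps patients unaware of their arm until they rate satisfaction, so partly avoidable expectation bias could enter this one secondary outcome

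*Protocol*

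**What the plan says.** - **Allocation.** Protocol 2.a: "Patients will be randomized via block randomization". Ratio, block size, concealment and masking are not described.
- **Control arm.** Protocol 1.a: "Ten patients will undergo standard of care without use of the TPAD device and also complete surveys".
- **Device use.** Protocol 2.a places it after the patient is asleep ("Following induction of general anesthesia, the patient is prepped and draped in sterile fashion") and ends it during the operation, once the primary trocar is in: "The suction is then released and the TPAD taken away from the operating field".
- **Patient rating.** Protocol 2.a: "The patient will participate in a questionnaire". Protocol 2.g: "Another secondary outcome measure includes patient questionnaire to assess satisfaction". Neither place gives a time point or says who administers it. Protocol 8.m limits active participation to the duration of surgery and 9.d ends the experiment there, so the time of the rating cannot be inferred from the schedule.
- **Analysis.** SAP, Statistical Methods: each surgeon and patient answer is tested by a Wilcoxon test against a theoretical median of 4.0, described as the best value. No significance level or sidedness is given, and no between-arm test of the questionnaires is described.
- **Masking.** Neither document mentions blinding or masking of patients, or delayed disclosure of the arm. Protocol 2.c rules out deception.

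**The concern.** Patients consent to a trial of a new device and then rate their satisfaction. If they know their arm when they answer, enthusiasm or wariness about the device, or disappointment at not receiving it, can move the rating independently of what the device did. Randomisation does not remove this, because the effect arises after allocation.

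The surgeon handles the device, so the primary outcome, the surgeon questionnaire, cannot be masked. The patient rating is different: the patient is anaesthetised for the whole time the device is in use and learns the arm only from staff, records or marks on the skin. Much of that exposure could be limited, and the plan as written takes no step to limit it. At stake is the interpretation of one subjective secondary outcome.

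**Working it through.** **1. Can the patient know the arm directly?** Protocol 2.a puts induction before device placement and removal during surgery. The patient therefore cannot see or feel the device in use. Knowledge of the arm can come only from disclosure or from later cues.

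**2. Do the documents control disclosure?** No. Nothing in Protocol 2.a, 2.g, 8.g or 9.c, or in the SAP, addresses it. The documents do not say that patients are told their arm either.

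**3. What cues would remain if disclosure were withheld?** Protocol 9.a.i lists one TPAD risk, and it is visible: "skin discoloration/bruising". Protocol 2.a also says that study conduct "may take non-identifiable photographs of the portion of the patients skin where the TPAD device acts", and 2.d includes post-operative images. These cues arise mainly in the TPAD arm.

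**4. How sensitive is the planned test?** The plan gives no power, effect size or SD, so there is no figure to reproduce. The check uses the SAP's own test.

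Inputs: reference value 4.0, the top of the scale (SAP); 10 per arm (Protocol 1.a and 2.g) or 15 per group (SAP). Assumptions: exact test, two-sided 0.05, each arm tested separately.

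Because 4.0 is the maximum, every answer either equals it or lies below it. With m answers below 4, all m signed ranks have the same sign. Under the null hypothesis the chance of that in one given direction is (1/2)^m, so

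p = 2 × (1/2)^m, whatever the arm size.

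| m | p |
|---|---|
| 4 | 2 × 0.0625 = 0.125 |
| 5 | 2 × 0.03125 = 0.0625 |
| 6 | 2 × 0.015625 = 0.031 |
| 7 | 2 × 0.0078125 = 0.016 |

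The boundary lies between five and six. If six patients in an arm score below 4 and one of them would have answered 4 with a different expectation (for example 4 in place of 3), p moves from 0.031 to 0.0625. The SAP does not say whether the test is exact. A normal approximation would move the boundary, but one answer would still separate the two sides of it.

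**5. What could a shift in the share of answers below 4 do?** The chance of p < 0.05 is P(X ≥ 6) with X ~ Binomial(n, q), where q is the share of answers below 4. All values of q are assumptions.

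| q | n = 10 | n = 15 |
|---|---|---|
| 0.40 | 0.166 | 0.597 |
| 0.30 | 0.047 | 0.278 |
| 0.20 | 0.006 | 0.061 |

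At 15 per group, a fall in q from 0.40 to 0.30 through favourable expectation would cut the chance of rejection from about 0.60 to 0.28. An unfavourable expectation would act the other way. These figures show sensitivity; they do not estimate the bias.

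**The case against.** **The documents do not show that bias occurs.** A reader might infer that patients are told their arm and that the rating is therefore biased. No section says so, and the consent form, where this might be settled, was not available. This stands: the supportable statement is that bias could enter.

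**Masking would be incomplete and not free.** A reader might infer that withholding the allocation removes the problem at no cost. It would not. Suction marks and site photographs can reveal the arm, mainly to device patients, so masking could fail unequally between arms. The documents give neither how often marks occur nor when the rating is made, so the gain cannot be quantified. This also stands: the bias is partly avoidable.

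**The effect should not be sized as a between-arm difference.** A reader might set an expectation effect against the standard error of a difference in arm means, SD × √(2/n). The SAP plans no such comparison and gives no SD. An assumed 0.3-point effect reaches one standard error only if the SD is at most 0.3/√(2/10) = 0.67 at 10 per arm, or 0.3/√(2/15) = 0.82 at 15, so even on that measure the result depends on assumptions. The one-sample check is the relevant one.

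**Little room at the ceiling.** If answers mostly sit at 4.0, as the SAP assumes, favourable expectation can raise few of them. This limits the upward effect but not the downward one.

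**This is an unpowered pilot with an unmaskable primary outcome.** True, and it keeps the point minor. But the plan chose to randomise, to survey controls and to test patient answers, so a simple protection remains worthwhile. The statement in 2.c that no deception is used is no barrier, because withholding the allocation with the patient's knowledge is not deception.

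**Conclusion.** The point holds in limited form. In the text available, nothing keeps patients unaware of their arm before they rate satisfaction, although the way the device is used makes this largely feasible. Expectation bias could enter this one secondary outcome; its size and direction are unknown, and it is only partly avoidable.

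The planned item-level test is sensitive to single answers: under an exact two-sided test at 0.05, the result turns on whether five or six patients score below 4. This rests on an assumed significance level, sidedness and exact calculation, and on each arm being tested separately, none of which the SAP states. The primary outcome is not affected. The point is a cheap improvement in conduct, not a flaw that undermines the trial.

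**What to change.** Add to Protocol 2.a:

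1. The allocation is not disclosed to the patient until the patient questionnaire is complete, and the consent discussion says so.
2. The questionnaire is given at one fixed, stated time point and in the same way in both arms. Protocol 8.m and 9.d should be made consistent with that time point.

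Optionally, ask each patient which arm they think they were in. With 10 to 15 patients per arm the answer would be imprecise, so it is an aid to interpretation and not a test of masking.

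Report the outcome as imperfectly masked. If masking is judged impractical, say in the protocol that the patient rating is open-label and interpret it accordingly.

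Cost: a sentence or two in the protocol, a matching line at consent and, if wanted, one extra question. No additional visit or procedure is needed. Patients learn their arm slightly later, and bruising or site photographs may still unmask some of them, mainly in the TPAD arm.
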